1 BACKGROUND

The clinical disease termed COVID-19 is caused by a novel betacorona virus, now named SARS-CoV-2. The most common symptoms being reported are fever, cough or chest tightness, and dyspnoea. Most cases are reported to experience a mild illness course (1). Thirty-two per cent required intensive care unit (ICU) admission for respiratory support (1). Laboratory features in this case series commonly included leukopenia, lymphopenia and raised aspartate aminotransferase (1). An epidemiological study of 99 cases of 2019 novel coronavirus pneumonia in Wuhan, China. found an overall mortality rate of 11% with 23% of patients requiring ICU admission (1). Currently, the World Health Organization (WHO) upgraded the status of the COVID-19 outbreak from epidemic to pandemic. In Saudi Arabia, the number of cases of infection with COVID-19 continues to be markedly increasing over the last couple of weeks (2).

Given no specific proven antiviral therapy or vaccination available for COVID-19, the Nigella sativa (NS) seed oil is suggested as a potential supplement due to its known immunostimulant and antiviral activities in previous published studies (3,4). Fortunately, NS oil is available as an oral softgel capsules in commercial pharmacies in Saudi Arabia and licensed by the Saudi Food and Drug Authority (SFDA).

NS (known as Black seed) in Latin language or "Habatulbarakah" in Arabic language, is a well-known food supplement and medicinal plant in the Arabic and Islamic culture. It is used as a food spice and it has plenty of medical claims that originate from different historical backgrounds. The seeds of NS contain several active compounds that have been isolated, identified and reported, most importantly thymoquinone.

In the literature, NS showed several pharmacological activities including antiinflammatory, anti-viral, and immunostimulatory activities (3,4).

1.1 Overview of Non-Clinical Studies

Regarding antiviral activity, NS oil was found to suppress viral load of Murine cytomegalovirus (MCNV) in infected mice to undetectable level in the liver and spleen in 10 days' intraperitoneal administration (5). This was possibly due to the increase in number and function of T cells and increased production of interferon-gamma. In addition, a review article discussed the potential antiviral activities of NS on different viruses including avian influenza (H9N2) in animal models. Interestingly, an in-vitro study showed the virus load decreased significantly when NS extract was added to the CoV infected cells and increased Interleukin-8 secretion (6).

Regarding immunostimulant activity, NS oil was found to exhibit nonspecific immunostimulant effect and able to induce cellular immune response as increasing lymphocytes pathogenesis and macrophage activities percent and macrophage index. It was found that it enhances T cells, natural killer cell activity and both interleukin-IB (IL-IB) and interleukine-3 (IL-3). Based on animal study, treatment with NS oil increased *the* phagocytic activity and phagocytic index of peritoneal macrophages and lymphocyte count in peripheral blood in diabetic hamsters (3). NS also reversed the Immunosuppression induced by lead and calcium in animal study. Based on laboratory study, a melanin extract from NS may induce the expression of three cytokines (TNF-alpha "Tumor necrosis factor").

alpha", IL-6 and VEGF "Vascular endothelial growth factor") that enhance immunogenicity (3).

Moreover, NS has also been shown to modulate the immune system by altering levels of inflammatory mediators (7). Also, due to other activities of NS such as anti-inflammatory, analgesic, antipyretic and bronchodilatation it may be beneficial to minimize the symptoms in COVID-19 patients (8,9,10).

2 STUDY RATIONALE

Today in the era of evidence-based medicine, it is hard to accept those traditional medical claims of medicinal plants without valid scientific experiments. Yet, it is important to rational the uses of these plants based on clinical evidence. Moreover, the world is currently facing a crisis because of this potentially fatal COVID-19 outbreak with no proven efficacy yet of any drug therapy, while vaccination is not expected until 2021. Therefore, this study is intended to evaluate the potential efficacy for using NS in patients with COVID-19

2.1 Risk / Benefit Assessment

Potential benefits to individual participant: Anti-inflammatory and immunodulatory effects to enhance the recovery from COVID-19

Herbal product quality and safety: The Black Seed capsules (Cuminmar) are manufactured according to high standards of herbal product manufacturing facility and under GMP guidelines by Marnys Company. This product is licensed in Saudi Arabia under the local regulations (Saudi Food and Drug Authority) ensuring the quality and safety of drugs and sold in Saudi community pharmacies.

Investigators and Patient Safety: All procedures including patient diagnosis, primary and secondary endpoints measurements will be carried by specialist fully qualified medical doctors pharmacist inside King Abdulaziz university's hospital.

3 STUDY OBJECTIVES

3.1 Primary Objective

The primary objective is to assess the clinical efficacy as measured by the change in clinical recovery period over the 10 days treatment period.

3.2 Secondary Objectives

Assess the effect of NS on COVID-19 symptoms recovery.

4 STUDY DESIGN

4.1 Study Overview

This is a single center, open-label, controlled, randomized, phase II clinical trial. 200 of subjects are planned. Each subject will be administered a single dose (500 mg) of study drug twice daily for 10 days. Subjects will be assigned to the treatments in random order. Evaluations will be taken daily for evaluationg symptoms imrovpment.

Screening data will be reviewed to determine subject eligibility. Subjects who meet all inclusion criteria and none of the exclusion criteria will be entered into the study.

The following treatment regimens will be used:

- Experimental treatment NS at the following dose 500 mg twice daily
- Comparator Standard care for COVID-19

Total duration of subject participation will be 14 days. Total duration of the study is expected to be 12 months.

5 CRITERIA FOR EVALUATION

5.1 Primary Efficacy Endpoint

Proportion of patients who clinically recovered (defined as 3 days of no symptoms) within 14 days after date of onset of symptoms.

5.2 Secondary Efficacy Endpoints

- Improvement of Clinical Parameters:
- o Time to full clinical recovery
- o Time to progression to pneumonia or hypoxia
- o Duration of illness
- o Discharge to home
- o Normalization of chest radiograph.

o Rate of complications: ICU admission, noninvasive ventilator, superadded infection o Death.

- Normalization of Routine Laboratory Tests:
- o Complete Blood Count (CBC)

o Erythrocyte sedimentation rate (ESR)

o C-reactive protein

o D-dimer

o Liver function test

o Renal function test

o Lactate Dehydrogenase (LDH),

o Immunoglobulins (IgA, IgE, IgG, IgM),

o Compliments (c3, c4),

o Chest X-ray, CT scan

o COVID-19 PCR

o Immune phenotype (CD3 T Cell, CD4 T Cell, CD8 T Cell, CD19 B Cell, CD20 B Cell, NK Cell)

- Additional:

o Inflammatory cytokines (IL-1β, IL-1Ra, IL-2, IL-6, IL-10, INF-alpha, INF-gamma, Eotaxin, RANTES & TNF-α).

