6 SUBJECT SELECTION

6.1 Study Population

Subjects with a diagnosis of mild to moderate COVID-19 who meet the inclusion and exclusion criteria will be eligible for participation in this study.

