6.2 Inclusion Criteria

-Patients with mild COVID19 (defined as upper respiratory tract infection symptoms in the absence of clinical or radiological signs of pneumonia).

-Adult (18 - 65 years old).

-Written informed consent by the patient (or legally authorized representative) prior to initiation of any study procedures.

-All patients should understand and agree to comply with planned study procedures. -Polymerase chain reaction (PCR)-confirmed infection with Severe Acute Respiratory Syndrome Coronavirus-2 (SARS-CoV-2).

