6.3 Exclusion Criteria

-Patients with pneumonia or severe illness requiring admission to intensive care unit. -Asymptomatic patients.

-Severe chronic kidney disease (i.e. estimated glomerular filtration rate [eGFR] < 30 mL/min) or end stage renal disease requiring dialysis

-Severe chronic liver disease (Alanine transaminase [AIT] or Aspartate transaminase [AST] > 5 times the upper limit of normal).

-Pregnancy or breast feeding.

-Anticipated transfer within 72 hours to another hospital that is not a study site.

-Allergy to the study medication.

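### The chest-film normalisation entries in 5.2 do not fit a population that 6.2 limits to patients without pneumonia (minor; secondary endpoints only)

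*Combined protocol and SAP*

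**What the plan says.** Section 5.2 (Secondary Efficacy Endpoints) contains two chest-imaging items. The first is "Normalization of chest radiograph", among the clinical parameters. The second is "Chest X-ray, CT scan", under the heading "Normalization of Routine Laboratory Tests". The synopsis repeats both. Section 5.2 also lists, separately, "Time to progression to pneumonia or hypoxia".

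The entry criteria bear directly on these items:

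- 6.2 defines eligible mild disease as "upper respiratory tract infection symptoms in the absence of clinical or radiological signs of pneumonia".
- 6.3 excludes "Patients with pneumonia or severe illness requiring admission to intensive care unit". The ICU phrase may or may not qualify pneumonia.
- 6.1 describes a wider severity range but keeps the criteria in force: "Subjects with a diagnosis of mild to moderate COVID-19 who meet the inclusion and exclusion criteria" are eligible.
- 4.1 says the same: "Subjects who meet all inclusion criteria and none of the exclusion criteria will be entered into the study".

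No section of the reviewed text defines normalisation, its denominator, the day of reading, or how a patient with a normal entry film counts. On analysis, 14.1 takes dosed subjects as the data set and 14.4 names the Student t test for secondary endpoints. Section 8.3 states that there is no control product. The procedures listed in Section 10 for Visit 1 and the 14-day monitoring name no film, but Section 9 places the schedule of tests in Appendix 1, which is not in the reviewed text.

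**The concern.** A film can normalise only if it was first abnormal. Under 6.2 no pneumonia abnormality is expected at entry, so the patients who can meet the endpoint are mainly those who worsen after randomisation. Whether a patient joins that group is an outcome, and one that treatment is meant to affect. Randomisation therefore does not protect a comparison made within it.

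Two distortions are possible. A proportion among patients with abnormal films can look equal in both arms although one arm had far less pneumonia. A raw count of normalisations can be higher in the arm with more pneumonia, because more patients there had something to clear. The trial is open-label, so a scoring rule chosen after the data are seen also leaves room for selective reporting.

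**Working it through.** **The text alone.** There are two readings of normalisation.

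1. *Abnormal becoming normal.* Sections 6.1 and 4.1 keep 6.2 in force, and 6.2 bars pneumonia however 6.3 is parsed. The scorable patients are then new pneumonia cases plus two exceptions: non-pneumonic abnormalities at entry, and pneumonia present at entry but not imaged.
2. *Film normal at the end of study.* Almost every patient meets this from entry and fails it only by developing pneumonia that has not cleared. It mainly repeats the progression endpoint.

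**Extent.** Section 5.2 has 7 clinical items, 12 under the laboratory heading and 1 cytokine line: 7 + 12 + 1 = 20. Two of the 20 are affected.

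**Size of the scorable group under reading 1.** The plan gives 100 per arm (14.5). It gives no pneumonia rate, so the rate q is assumed. Scorable patients per arm = 100 × q, that is 2, 5, 10 and 20 at q = 2%, 5%, 10% and 20%. Take a large difference in clearance, 30% against 70%. Approximate power is Φ[(0.4√n − 1.96√(2 × 0.5 × 0.5)) / √(0.3 × 0.7 + 0.7 × 0.3)]. At n = 10 this is Φ[(1.265 − 1.386)/0.648] = Φ(−0.187) = 43%. At n = 2, 5 and 20 it is 10%, 22% and 73%.

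**Direction of the result.** Further assumptions: NS halves pneumonia, and 40% of cases clear by Day 14 in both arms. Three scorings:

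- (A) normalisations over all randomised = cases × clearance
- (B) proportion among abnormal films = clearance
- (C) free of a pneumonia abnormality at Day 14 = 100 − cases × (1 − clearance)

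| Control pneumonia | Cases, control v NS | (A) | (B) | (C) |
|---|---|---|---|---|
| 5% | 5 v 2.5 | 2 v 1 | 40% v 40% | 97 v 98.5 |
| 10% | 10 v 5 | 4 v 2 | 40% v 40% | 94 v 97 |
| 20% | 20 v 10 | 8 v 4 | 40% v 40% | 88 v 94 |

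(A) favours the worse arm, (B) shows nothing and (C) favours the better arm. In the 10% row, (B) compares 4/10 (exact 95% CI 12% to 74%) with 2/5 (5% to 85%).

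**Sensitivity of (A).** It favours control whenever the NS/control pneumonia ratio times the NS/control clearance ratio is below 1. In the 10% row:

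- equal clearance of 20%, 40% or 60%: 2 v 1, 4 v 2, 6 v 3
- clearance 40% control, 60% NS: 10 × 0.4 = 4 v 5 × 0.6 = 3
- clearance 40% control, 80% NS: 4 v 4, a tie; it reverses only above that

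**Which all-randomised outcome is more informative.** Two-sided Fisher exact power at 0.05, 100 per arm, for the 10% and 20% rows:

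- (C), 94 v 97 and 88 v 94: 9% and 24%
- simple pneumonia incidence, 10% v 5% and 20% v 10%: 19% and 44%

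Incidence does better under the same assumptions, but neither has adequate power.

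**The case against.** The strongest reply is that the criticism depends on a reading the protocol does not state. If the endpoint means a normal film at the end of study, everyone imaged can be scored and the result points the right way, as (C) shows. Scoring (A), the only one that favours the worse arm, appears nowhere in the documents. The pneumonia and clearance rates are assumed. A difference in pneumonia would in any case be looked for under the separate progression endpoint, and the trial is an exploratory phase II whose primary endpoint is symptom recovery.

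Most of this stands, and it limits the point to a minor one. It does not remove it. The ordinary sense gives a subset chosen by outcome and the alternative gives near-duplication, so the entry fits the population poorly either way.

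A reader might infer more than the documents support:

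- *That the endpoint cannot be scored at all.* Non-pneumonic abnormalities and unimaged pneumonia at entry leave some patients scorable under reading 1, and reading 2 covers everyone imaged.
- *That the trial would be biased towards the worse arm.* That needs scoring (A), which the plan does not adopt.
- *That no films are planned because Section 10 names none.* Section 10 is not exhaustive: it also omits the physical examination in 9.1.4. The schedule is in Appendix 1, which was not available. For the same reason nothing is claimed here about the laboratory endpoints.

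**Conclusion.** The mismatch between 5.2 and 6.2 is real, and it goes beyond a missing definition: the endpoint does not suit the patients admitted. Its importance is minor. It affects two overlapping entries among 20 secondary items, progression to pneumonia is already listed, and the primary endpoint is untouched.

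The textual conclusion rests on 6.2 being applied as written. If 6.1 signals that pneumonia at entry was meant to be allowed, normalisation would have a baseline group to act on, and the entry criteria would be what needs correcting. The numbers show only how the scoring rule can set the direction of the result. They predict nothing about this trial, since every pneumonia and clearance rate in them is assumed.

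**What to change.** Preferred: delete both imaging-normalisation entries from 5.2 and the synopsis, and rely on "Time to progression to pneumonia or hypoxia". Analyse it by randomised arm in all randomised patients, with one written ascertainment rule applied identically in both arms.

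Alternative, if an imaging endpoint is wanted: redefine it as the proportion with new radiographic pneumonia by Day 14 among all randomised patients. State how patients not imaged and deaths are counted, and report it descriptively with a confidence interval.

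Either choice needs matching changes elsewhere:

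- 14.1: replace the dosed-subjects data set for this analysis. Read literally it leaves out controls, who receive no product.
- 14.4: replace the Student t test for this endpoint. It is unsuited to a proportion or a time to event.
- 6.1, 6.2 and 6.3: reconcile them on whether pneumonia at entry is allowed.

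Cost: mainly wording. One exploratory secondary endpoint is lost or redefined. If Appendix 1 does not already schedule equal ascertainment in both arms, the progression endpoint may need an added procedure, and the alternative needs either a film in each patient or the stated rule for those not imaged.

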8 STUDY TREATMENTS

8.1 Method of Assigning Subjects to Treatment Groups

Up to 200 eligible patients will be randomly assigned to treatment or control groups in a 1:1 ratio using a computer-generated randomization scheme developed by http://www.randomization.com.

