14.4 Analysis of Secondary Endpoints

Student t test will be used for significance analysis.

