14.5 Sample Size and Randomization

To achieve a power of 80% and a two-tailed p-value of <0.05 of an assumed 40% difference between the proportion of patients with clinical cure among the NS group in comparison with the control group, a total of at least 200 patients assigned randomly into the two arms (ie 100 patients per arm) will be needed to be included in the study as

calculated using G*Power version 3.1.9.2 (Heinrich-Heine-University Düsseldorf, Düsseldorf, Germany).

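### The t test named for rare yes/no outcomes (ICU admission, ventilation, superadded infection, death) is unsuitable and has no result at 0 v 0; name a binary-data method instead (minor)

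*Combined protocol and SAP*

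**What the plan says.** Section 5.2 includes among the secondary endpoints "Rate of complications: ICU admission, noninvasive ventilator, superadded infection", followed by death. Section 14.4 is a single sentence: "Student t test will be used for significance analysis". It makes no exception for binary outcomes. It names no effect measure, no confidence interval and no rule for few or zero events. No test for proportions is named elsewhere; the synopsis statistics entry also refers to a t test, for comparing group means.

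Four other statements bear on the point:

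- **Population (6.2):** entry is limited to "Patients with mild COVID19 (defined as upper respiratory tract infection symptoms in the absence of clinical or radiological signs of pneumonia"), in adults up to age 65. Section 6.3 excludes pneumonia and severe illness needing intensive care.
- **Follow-up (4.1):** "Total duration of subject participation will be 14 days".
- **Numbers (14.5 and 8.1):** "ie 100 patients per arm", "randomly assigned to treatment or control groups in a 1:1 ratio".
- **Significance level (14.5):** "To achieve a power of 80% and a two-tailed p-value of <0.05" appears in the sample-size statement. No level is given for the secondary endpoints.

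**The concern.** A t test compares means of a roughly continuous measure. ICU admission, ventilation, superadded infection and death are each 0 or 1 per patient. In this population the counts could easily be zero to a few per arm. Two things follow if 14.4 is applied as written.

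First, with no events in either arm the pooled variance is zero, so the planned analysis returns nothing. The plan does not say what happens then.

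Second, with a handful of events, whether p falls below 0.05 can turn on the choice of test. An analyst who sees an empty or borderline result and changes method would be choosing after seeing the data, in an open-label trial. ICU transfer is also a safety measure (section 5.3), so these outcomes will be read with care.

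**Working it through.** **Inputs.** There are 100 patients per arm, 1:1 (sections 14.5 and 8.1). A two-sided 0.05 level is assumed for secondary endpoints, because the documents state it only for the sample size. Event rates of 0.5% to 5% are assumptions; the documents give none. There is no plan figure for these endpoints to reproduce. The planned 100 per arm is taken as given, and its derivation is a separate matter.

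**1. The t test at 4 v 0.**
- Risk difference = 4/100 − 0/100 = 0.04.
- Sample variances: 0.04 × 0.96 × 100/99 = 0.03879 in one arm and 0 in the other. Pooled variance = 0.03879/2 = 0.01939.
- Standard error = √(0.01939 × 2/100) = 0.01969.
- t = 0.04/0.01969 = 2.031 on 198 df, two-sided p = 0.0436.

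This is the smallest k v 0 split that the t test calls significant; at 3 v 0, p = 0.082. The same threshold of four events holds at 80, 90 and 110 per arm.

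**2. Other tests on the same tables (p-values).**

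| Events | Student t | Barnard | Boschloo | Fisher |
|---|---|---|---|---|
| 4 v 0 | 0.044 | 0.046 | 0.104 | 0.121 |
| 5 v 0 | 0.024 | 0.026 | 0.044 | 0.059 |
| 6 v 0 | 0.013 | 0.013 | 0.020 | 0.029 |
| 7 v 1 | 0.030 | 0.035 | 0.051 | 0.065 |

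Barnard, Boschloo and Fisher are all exact tests, and they do not agree with one another. Barnard sides with the t test in every row. Boschloo sides with it at 5 v 0 and 6 v 0. Fisher first falls below 0.05 at 6 v 0.

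**3. How often this matters.** Among tables with 10 or fewer events in total, the t test and Fisher fall on opposite sides of 0.05 in three distinct splits: 4 v 0, 5 v 0 and 7 v 1. If the arms have equal rates, the chance of any such disagreement is 1.3% at a 1% event rate and 3.5% at 2%.

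**4. No events in either arm.** Difference = 0 and pooled variance = 0, so t = 0/0. The chance of this is (1 − p)^200:
- p = 0.5%: 0.995^200 = 0.367
- p = 1%: 0.99^200 = 0.134
- p = 2%: 0.98^200 = 0.018

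**5. Exact type I error of the t test**, by summing the two binomial distributions over all tables at 100 per arm:

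| Event rate | t test | Fisher |
|---|---|---|
| 1% | 1.4% | 0.04% |
| 2% | 4.0% | 0.5% |
| 3% | 4.5% | 1.1% |
| 5% | 4.4% | 2.1% |

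For any event rate up to 5%, the t test's maximum is 4.5%. It is 5.2% at a 10% rate, and the maximum over all rates is 5.6%, at 50%.

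**6. What an interval would report.** The Newcombe interval combines the Wilson limits of the two arms. For 0/100, with z² = 3.8415, the Wilson limits are 0 and z²/(n + z²) = 3.8415/103.8415 = 0.037. At 0 v 0 the interval for the risk difference is therefore −3.7 to +3.7 percentage points. At 4 v 0, the Wilson limits for 4/100 are 0.0157 and 0.0984:
- lower limit = 0.04 − √((0.04 − 0.0157)² + 0.037²) = −0.004
- upper limit = 0.04 + (0.0984 − 0.04) = 0.098

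That is −0.4 to +9.8 points. Both tables give a usable result.

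**The case against.** A reader might infer from the 4 v 0 example that the t test manufactures significance which exact methods reject. The documents and the arithmetic do not support that. Barnard's exact test is below 0.05 at 4 v 0, 5 v 0 and 7 v 1, as the t test is. The t test's exact error rate stays under 5% at the low event rates that matter here. To call its p-value wrong is to take Fisher's as the truth, and Fisher's error rate at these event rates is only 0.04% to 2.1%. This objection stands in full.

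A reader might also count every table where the t test and Fisher disagree. There are 186 at 100 per arm, but that covers all event rates and both mirror images. Only three distinct splits have 10 or fewer events, so the count says little about sparse outcomes.

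The setting is partly assumed. No complication rates are given, superadded infection need not be as rare as death, and section 6.1 speaks of mild to moderate disease, although still subject to the entry criteria. The synopsis calls the trial exploratory, so a nominal p-value on these endpoints may carry little weight. This too stands, and it limits the severity.

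Finally, one can say that 0 v 0 changes no conclusion, since the counts speak for themselves and Fisher's p is 1. That is true of the p-value. But the plan promises neither counts nor an interval, and a bound of about 3.7 points either way is information that the stated analysis cannot give.

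**Conclusion.** The point holds as a minor one. The only method stated for four yes/no endpoints is a test of means, which does not suit them and has no value when neither arm has an event. That empty result has a probability of 13% at a 1% event rate and 37% at 0.5%. Where events are few, a result near 0.05 depends on which test is used, with p from 0.044 to 0.121 at 4 v 0. The finding is not one of excess false positives.

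It rests on 100 analysed per arm, a two-sided 0.05 level carried over from the sample-size statement, and rarity inferred from mild disease and 14 days of participation. If events turn out to be common, the zero-event problem disappears and the argument reduces to choosing a method that suits proportions.

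**What to change.** In section 14.4, remove the t test for these endpoints and state, for example: *ICU admission, noninvasive ventilation, superadded infection and death will be reported as counts and percentages by arm, with a Newcombe 95% confidence interval for the risk difference, including when no events occur, and a two-sided Fisher exact test.* An exact interval would serve equally well. So would an unconditional exact test such as Barnard or Boschloo, provided that one is named before the data are seen.

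The cost is a sentence or two. If Fisher is chosen, it is conservative, so a few borderline results (4 v 0, 5 v 0 and 7 v 1 among the sparse tables) would no longer be called significant.
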